Aim 1: To compare the effectiveness of modafinil and amphetamine salts in patients with narcolepsy type 2 or idiopathic hypersomnia. The primary outcome will be the change in Epworth Sleepiness Scale score from pre-treatment baseline. Secondary outcomes will include Patient Global Impression of Change from baseline for sleepiness, sleep inertia, and cognitive dysfunction.

Aim 2: To compare the safety of modafinil and amphetamine salts in the treatment of narcolepsy type 2 or idiopathic hypersomnia.

Aim 3: To evaluate for clinical predictors of response to modafinil and amphetamine salts in these patients.

Study Design & Methods

Treatment-naïve adult patients (n = 44), or adult patients free of wake-promoting medication or willing to discontinue current wake-promoting medication seeking evaluation at the Emory Sleep Center for narcolepsy type 2 or idiopathic hypersomnia will be invited to participate and randomized to one of the treatment arms upon consent. Although pragmatic trials often do not involve blinding to condition, those trials where outcomes of interest are primarily subjective often require blinding to minimize bias (20), which will be necessary in this case. Randomization, allocation concealment, blinding, and medication dispensing will be managed by Emory's Investigational Drug Service (IDS). The IDS will use 1:1 computer generated randomization (23), with a block design to ensure equal number of participants receiving each study medication. Block size will not be disclosed to the study investigators or staff. Identity of medications will be concealed by the pharmacy using matched pills and pill containers. The IDS is located in a separate building from the study team and will have no interaction with participants. Medications will be transferred from the pharmacy via courier. This protocol will be approved by the Emory University Institutional Review Board and registered at clinicaltrials.gov prior to enrollment of the first participant.

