Participants will be randomized to receive a 12-week treatment course with either modafinil or amphetamine-dextroamphetamine. Both are US FDA approved for the treatment of narcolepsy, although are considered off-label use for idiopathic hypersomnia. The main risks of participation are from the study medications (which are the standard of care). Common adverse events include: headache, nervousness, anxiety, insomnia, anorexia, xerostomia, palpitations/tachycardia, emotional lability, agitation. Less commonly reported adverse events included: nausea/vomiting, rhinitis, diarrhea, dizziness, dyspepsia, pharyngitis, HTN, chest pain, vasodilation, elevated ALT or AST, paresthesia, depression, constipation, abdominal pain, weight loss, motor/phonic tic exacerbation, dyspnea, diaphoresis, dysmenorrhea, impotence, visual disturbance, restlessness, tooth disorder, photosensitivity. Rare but serious AEs include:

- dependency, abuse
- psychosis
- mania
- aggressive behavior
- sudden death
- myocardial infarction
- stroke
- HTN
- cardiomyopathy (long-term use)
- seizures
- hypersensitive reaction, multi organ
- anaphylaxis
- Stevens-Johnson syndrome

- toxic epidermal necrolysis
- priapism
- peripheral vasculopathy
- Raynaud phenomenon
- Growth suppression (long-term use, peds pts)
- rhabdomyolysis
- withdrawal signs and symptoms if abrupt discontinuation (prolonged with high dose use)
- angioedema
- drug reaction with eosinophilia and systematic signs and symptoms
- hallucinations
- suicidal ideation

However, the medications being used in this study are currently standard of care for narcolepsy, being tested in this study for equivalency. Therefore, although there are risks to participation in this research, they are of the same magnitude of the risks patients take when seeking treatment for these disorders outside of this research. The benefit to be gained is a clearer understanding of the relative risks and benefits of these medications and the clinical features that can help predict response to treatment.

Community Participation

[name] consulted with leadership from the Hypersomnia Foundation and Narcolepsy Network in the initial submission of this work and will present results from the study at at least one meeting of one or both of these patient organizations following its completion.

Participant Selection

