This study will recruit up to 55 participants, with a sample size target of 44 participants who complete participation in the 12 week medication trial. Participants will be newly diagnosed, medication-naïve individuals, or formerly diagnosed, free of wake-promoting medication or willing to discontinue current wake-promoting medication with diagnoses of: narcolepsy type 2 or idiopathic hypersomnia.

Inclusion criteria will be: 1) narcolepsy type 2 or idiopathic hypersomnia; 2) age 18-65; 3) informed consent.

Exclusion criteria will be: 1) contraindication to modafinil or amphetamine salts (history of left ventricular hypertrophy, mitral valve prolapse, other cardiac structural abnormalities, severe cardiovascular disease, unstable angina, myocardial infarction, cardiomyopathy, severe arrhythmias, uncontrolled hypertension, severe hepatic impairment, substance abuse history, psychosis, glaucoma, Tourette's syndrome, and epilepsy); 2) obstructive sleep apnea (AHI > 15); 3) severe periodic limb movements of sleep with arousals (PLM arousal index > 30); 4) allergy to either of the study drugs; and 4) pregnancy or breastfeeding.

Participants who withdraw from study medication will be invited to complete remaining questionnaires/study visits.

Visit Schedule

Visit 1: Enrollment: After reviewing information about the study and confirming participation, subjects will answer questions about their sleep disorder and the symptoms experienced. This visit is expected to last about one hour. If participants are suspected of having a diagnosis of narcolepsy type 2 or idiopathic hypersomnia and have never had an overnight polysomnogram (PSG) and next-day MSLT, they will be scheduled for an

additional study visit to complete a PSG and MSLT before visit 3. If participants already have a confirmed diagnosis of narcolepsy type 2 or idiopathic hypersomnia and are taking certain stimulant medications they will be asked to wean off of this medication before and during the study. After weaning off of medicines, the participant will be given a four-week supply of one of the two study medications. The medication will be provided will be assigned randomly, the participant and the doctor will not be told which of the two study medications are given.

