APPENDIX 1. SCHEDULE OF STUDY VISITS

	VISIT 1	VISIT 2 – SLEEP STUDY	VISIT 3	VISIT 4	VISIT 5
Informed Consent	X				
Medical History	X				
Study Inclusion/Exclusion	X				
Concomitant Medication Review	X	X	X	X	X
Wean off current wake- promoting medicines	X				
Adverse Experiences		X	X	X	X
Participant Payment	X				X
PSG/MSLT sleep study		X			
Sleepy Packet	X				
Sleep Inertia Questionnaire	X	X	X	X	X
Epworth Severity Scale	X	X	X	X	X
CGI- Baseline Questionnaire	X	X	X	X	X
CGI- Sleep Inertia Questionnaire	X	X	X	X	X
CGI- Sleepiness Questionnaire	X	X	X	X	X
CGI- Cognitive Dysfunction Questionnaire	X	X	X	X	X
Treatment Questionnaire	X	-	X	X	X
Treatment Comparison Questionnaire	X	-	X	X	X
Study Drug Titration Reviewed	X				
Randomization	X	OR X			
Dispensing or Administration of Study Drug	X	OR X	X	X	
Counting of Returned Study Drug			X	X	X

Informed Consent Process

Consent will be obtained in-person from a study PI, co-I, or coordinator. Comprehension will be ensured by allowing ample time for questions and discussion and verbally reviewing the information with the subject in addition to reviewing the written consent form. The discussion will take place at the Emory Sleep Center.

Compensation

Participants will be compensated \$25 for visit 1 (enrollment) and \$25.00 for the week 12 study visit (visit 5), for a total of \$50.

Statistical Analysis

Sample size will be 22 in each group. This sample size is sufficient to demonstrate a reduction in ESS of 4 points with amphetamine salts, assuming a standard deviation of change from baseline of 6.2 (35). This is

a conservative, but clinically significant, change in Epworth, compared to the observed change from baseline of 5.3 points in clinical trials of modafinil [weighted average from (15, 35, 36)]. This sample size provides 82.8% power to find a moderately large effect size for amphetamine salts. For non-inferiority, we will use a responder definition of those achieving a 25% reduction in ESS, a data-driven minimal clinically significant change in patients with narcolepsy (29). Assuming 80% of participants meet this threshold, 22 participants per group will provide 80% power to a non-inferiority limit of 30% (37, 38).

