Intention-to-treat analyses will be performed, using last observation carried forward in the event of participant drop-out. The change in ESS at week 12 from baseline will be compared between the two treatment groups via t-test (compared for unequal variances if necessary) and will be evaluated on a hypothesis of non-inferiority. Similar analyses will be performed on secondary outcomes, considering the proportion of responders in each treatment arm who rate themselves "much improved" or "very much improved". Categorical outcomes, including these PGI-C proportions and adverse events, will be compared using Chisquare or Fisher exact test. Exploratory analyses will evaluate response at week 4 and week 8 between the two medications groups, to determine if there is a difference in time to symptom control.

Considering each medication separately, predictors of response will be assessed using logistic regression. The main predictor of interest will be hypersomnia diagnosis, i.e., narcolepsy type 2 or idiopathic hypersomnia. Other predictors, to be considered in separate, exploratory regression models, include: MSLT mean sleep latency, MSLT number of SOREMs, sex/gender, baseline ESS, age, and comorbidities. Significant predictors in univariate models will be combined in a multivariate model. Although the investigative team has extensive clinical trial and statistical experience, additional statistical consultation will be provided as needed through Emory's CTSA consultation program.

Data Safety Monitoring and Reporting

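### Aim 2's safety comparison is a chi-square or Fisher test with 22 per arm and no effect estimate or interval, so a non-significant result could be misread as similar safety

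*Combined protocol and SAP*

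**What the plan says.** The Objectives section states the second aim as "To compare the safety of modafinil and amphetamine salts in the treatment of narcolepsy type 2 or idiopathic hypersomnia". The Abstract says that all three aims are meant to inform the choice between the drugs.

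Under Statistical Analysis, one clause covers this aim: "Categorical outcomes, including these PGI-C proportions and adverse events, will be compared using Chisquare or Fisher exact test". That section names no risk difference, confidence interval or tolerated excess for safety, and no rule for reading a non-significant result. Data Safety Monitoring and Reporting covers review and reporting of individual events, not a comparison of the arms.

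The sample size statement, "Sample size will be 22 in each group", is supported only by the Epworth Sleepiness Scale (ESS). Participant Selection adds: "This study will recruit up to 55 participants, with a sample size target of 44 participants who complete participation".

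In the discussion of risks, Study Design & Methods says that "the medications being used in this study are currently standard of care for narcolepsy, being tested in this study for equivalency". It lists adverse events without rates.

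**The concern.** A test of no difference answers one question: are the data incompatible with equal event rates? With 22 per arm they can be compatible with equal rates and also with a large excess on one drug. A p-value alone does not show this; an interval does.

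This matters more here than in a routine safety table, because safety is a named aim intended to guide treatment choice. For ESS the plan sets a non-inferiority hypothesis; for safety it sets nothing comparable. If ESS is found non-inferior and the report adds that adverse events did not differ significantly, a reader could take the drugs as interchangeable when the safety data cannot support that.

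**Working it through.** **The plan's own figures.** No power is stated for safety. The two stated figures concern efficacy:
- Responder non-inferiority (80% responders, 30-point limit, 80% power): n = (1.645 + 0.842)² × 2 × 0.8 × 0.2 / 0.30² = 22.0 per arm. This reproduces the plan's 22 at one-sided 5%.
- 82.8% for a 4-point ESS change with SD 6.2: a within-arm t-test with n = 22 at two-sided 5% gives 82.3%, which is close.

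Neither bears on adverse events.

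**Inputs for safety.**
- From the documents: 22 per arm, 1:1 allocation, chi-square or Fisher test, at most 55 recruits (about 27 per arm).
- Assumed: two-sided 5%, and the event rates.

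**Chance of missing a true difference.** For every pair (x, y) with x and y from 0 to 22, the probability is Bin(x; 22, p1) × Bin(y; 22, p2). Summing over the pairs with p ≥ 0.05 gives the miss rate:

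| Assumed true rates | Chi-square (uncorrected) | Fisher |
|---|---|---|
| 10% v 20% | 85% | 92% |
| 5% v 20% | 67% | 80% |
| 10% v 30% | 61% | 72% |
| 20% v 40% | 70% | 79% |
| 30% v 60% | 48% | 60% |
| 20% v 50% | 45% | 57% |
| 20% v 60% | 21% | 31% |

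Check for 20% v 40% by normal approximation:
- Standard error under no difference: √(2 × 0.3 × 0.7 / 22) = 0.138.
- Standard error under the assumed rates: √((0.2 × 0.8 + 0.4 × 0.6) / 22) = 0.135.
- Power = Φ((0.20 - 1.96 × 0.138) / 0.135) = Φ(-0.525) = 30%, so 70% are missed.

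With 27 per arm the same enumeration gives 62% (chi-square) and 74% (Fisher) for 20% v 40%.

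**What an interval would show.** The Newcombe interval for d = p1 - p2 combines the Wilson limits (l, u) of each arm:
- lower = d - √((p1 - l1)² + (u2 - p2)²)
- upper = d + √((u1 - p1)² + (p2 - l2)²)

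The Wilson 95% limits are 7.3% to 38.5% for 4/22 (18.2%) and 23.3% to 61.3% for 9/22 (40.9%).
- 9/22 v 4/22: d = 22.7 points. Lower = 22.7 - √(17.7² + 20.3²) = -4 points; upper = 22.7 + √(20.4² + 10.9²) = +46 points. The p-value is 0.19 by Fisher and 0.10 by uncorrected chi-square. Neither test is significant, yet an excess of more than 40 points is not excluded.
- 4/22 v 4/22: d = 0, limits ±√(20.3² + 10.9²) = ±23 points. Both tests give p = 1.0.
- 0/22 in one arm: the exact one-sided 95% upper limit is 1 - 0.05^(1/22) = 12.7%.

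**The case against.** **Low power for adverse events is ordinary in a 44-person trial sized on its primary outcome.** This stands. It is not a reason to enlarge the trial: 80% power for 20% v 40% at two-sided 5% would take 82 per arm. The correctable part is the form in which the result is reported.

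**A reader might infer that the plan intends to treat non-significance as equal safety.** The documents do not support that. Aim 2 is worded as a comparison, the non-inferiority hypothesis is attached to ESS, and no safety equivalence hypothesis is stated. The word equivalency comes in a paragraph arguing that the risks match those of usual care, and that paragraph also promises clearer knowledge of relative risks. It makes a misreading easier; it does not commit the plan to one.

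**A reader might also infer that a non-significant result is to be expected whenever one drug is clearly worse tolerated.** The table does not bear this out: at 20% v 50% chi-square misses 45%, so significance is the likelier result, and at 20% v 60% only 21% to 31% are missed. The problem lies with moderate differences.

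**The figures lean pessimistic.** In part. All rates and the significance level are assumed. The plan allows either test, and chi-square is the more favourable. Analysing everyone recruited would add people, though 27 per arm is an upper bound because those with negative sleep testing are withdrawn. Even there, most trials would miss 20% v 40%.

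**A formal similarity margin would achieve little.** Agreed. With identical observed rates of 4/22 the interval already reaches 23 points. Nor do the documents specify recording the reason for stopping study drug or a severity scale, so a lead endpoint built on either could not be assumed to need no new data.

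**Conclusion.** The point holds as a cheap improvement to the analysis. The stated method for Aim 2 gives a p-value and nothing that shows which safety differences remain compatible with the data. Under two-sided 5% and assumed rates of 20% and 40%, it would miss the difference in about 70% (chi-square) to 79% (Fisher) of trials at 22 per arm, and in 62% to 74% at about 27. Those percentages depend on rates that the documents do not give; smaller miss rates apply to larger differences. The absence of an estimate, an interval and a reading rule does not depend on them. The conclusion is that a non-significant result could be misread as similar safety. It is not that the sponsor plans such a reading, nor that the sample size must change.

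**What to change.** Under Statistical Analysis:

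1. Report each adverse event comparison (any event, and each event listed as common) as a risk difference between arms with a 95% Newcombe or Miettinen-Nurminen interval.
2. Where an arm has no events, give the exact upper limit for that arm's rate.
3. Keep the chi-square or Fisher p-value, if wanted, as a supplement.
4. State that a non-significant p-value will not be taken as evidence of similar safety, and that Aim 2 conclusions rest on the intervals.

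This needs only event counts per arm, so no new data, visits or participants. It costs a little more tabulation. The intervals will be wide, as the 4/22 v 4/22 example shows, and the Aim 2 conclusion will often be less favourable than a bare statement of no significant difference.

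### The PGI-C responder outcomes are tied to a non-inferiority framework but are given only tests of equality, with no margin or confidence interval

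*Combined protocol and SAP*

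**What the plan says.** Three consecutive statements in the Statistical Analysis section matter here.

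- The week-12 change in ESS is compared by t-test and "will be evaluated on a hypothesis of non-inferiority".
- The plan then turns to the PGI-C measures: "Similar analyses will be performed on secondary outcomes, considering the proportion of responders in each treatment arm", where a responder is a participant in the top two improvement categories of the PGI-C.
- The PGI-C proportions, grouped with adverse events as categorical outcomes, "will be compared using Chisquare or Fisher exact test".

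No margin, confidence interval, significance level or decision rule is given for any of the three PGI-C outcomes (sleepiness, sleep inertia, cognitive dysfunction).

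The only margin in the plan is in the sample-size paragraph of the same section, and it belongs to a different endpoint: "For non-inferiority, we will use a responder definition of those achieving a 25% reduction in ESS". The paragraph continues "Assuming 80% of participants meet this threshold", and then "22 participants per group will provide 80% power to a non-inferiority limit of 30" per cent. The risk discussion in Study Design & Methods also describes the two drugs as being tested for equivalence.

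**The concern.** Chi-square and Fisher tests ask whether the two proportions differ. Rejection shows a difference. Failure to reject shows only that the data did not establish one, and with about 22 participants per arm that is common even when the true difference is large. Showing that one drug is not worse than the other by more than a tolerable amount requires a stated amount and a confidence limit to set against it, and the plan supplies neither for PGI-C.

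The PGI-C outcomes are not minor in this trial. The Background and the outcome description present sleep inertia and cognitive dysfunction as symptoms that matter greatly to patients, and the Abstract says the results should inform shared treatment decisions. Under the plan as written, each PGI-C outcome yields either a significant difference or a p-value above 0.05 that cannot be interpreted as similarity. In a trial described in terms of non-inferiority and equivalence, readers could easily take the second result as reassurance.

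**Working it through.** **Inputs.** From the Statistical Analysis section: "Sample size will be 22 in each group", an 80% responder rate and a 30-point limit, both for ESS responders. From Participant Selection: recruitment of up to 55, so 55 / 2 = 27.5, taken as 27 per arm for a sensitivity case. Assumed here: a two-sided 5% level for the difference tests (the plan states none), and PGI-C rates 30 points apart (the plan gives no PGI-C rate).

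**Step 1: reproduce the plan's own figure.** For equal rates of 0.80 and a limit of 0.30, the standard error is √(2 × 0.8 × 0.2 / 22) = 0.1206, and 0.30 / 0.1206 = 2.487.

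- One-sided 5%: Φ(2.487 − 1.645) = Φ(0.842) = 80.0%. This matches the stated power.
- One-sided 2.5%: Φ(2.487 − 1.960) = Φ(0.527) = 70.1%. This does not match; 28 per arm would be needed.

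The sample-size statement therefore rests on a margin and a one-sided limit. No such rule is carried over to the PGI-C analysis.

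**Step 2: how often the named tests are non-significant at a 30-point deficit.** For 80% versus 50% by normal approximation, the mean rate is 0.65. The null standard error is √(2 × 0.65 × 0.35 / 22) = 0.1438, and the alternative standard error is √((0.16 + 0.25) / 22) = 0.1365. The probability of non-significance is Φ((1.96 × 0.1438 − 0.30) / 0.1365) = Φ(−0.133) = 44.7%.

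Exact figures come from summing the binomial probability of every 2 × 2 table with p > 0.05 (23 × 23 tables at 22 per arm; chi-square without continuity correction):

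| True rates | Per arm | Chi-square | Fisher |
|---|---|---|---|
| 80% v 50% | 22 | 45.0% | 56.8% |
| 90% v 60%, or 40% v 10% | 22 | 33.5% | 45.4% |
| 70% v 40%, or 60% v 30% | 22 | 47.9% | 60.3% |
| 65% v 35% | 22 | 48.1% | 60.5% |
| 80% v 50% | 27 | 34.3% | 45.0% |

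If the true rates are equal (80% or 50% in both arms, 22 per arm), the same tests are non-significant in about 95% to 98% of trials. A p-value above 0.05 is therefore the usual result when the drugs are alike, and is still common when one is 30 points worse.

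**Step 3: a confidence-limit rule for comparison.** Suppose non-inferiority is declared only when the lower one-sided 95% Wald limit for the difference lies above −30 points. A drug truly at 50% against 80% would pass in 5.1% of trials at 22 per arm. With equal rates the rule succeeds in 82% of trials at 80% and 67% at 50%. The 5.1% is a type I error and the figures in Step 2 are type II errors of a different test. They compare directly only if p > 0.05 is treated as a demonstration of non-inferiority.

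**Step 4: one table.** Take 18/22 against 11/22 responders, an observed deficit of 7/22 = 32 points.

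- Chi-square: 44 × (18 × 11 − 4 × 11)² / (29 × 15 × 22 × 22) = 4.96, p = 0.026. Fisher: p = 0.055. The two permitted tests fall on opposite sides of 0.05.
- Newcombe 95% interval: the Wilson limits are 0.615 to 0.927 for 18/22 and 0.307 to 0.693 for 11/22. The lower bound is −0.318 − √(0.193² + 0.109²) = −0.54 and the upper bound is −0.318 + √(0.193² + 0.203²) = −0.04.

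The interval, from −54 to −4 points, shows at once that these data do not support similarity. A bare Fisher p-value of 0.055 does not.

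**The case against.** The strongest reply is that a difference test may be exactly what was meant. The non-inferiority clause is attached to the ESS change. Similar analyses may mean no more than the same between-arm comparison under intention to treat. The next sentence groups PGI-C with adverse events, which carry no non-inferiority hypothesis. Aim 1 speaks of comparing effectiveness, and the Background wants these symptoms assessed for differential response. This reading is tenable. It does not remove the problem, because the plan then leaves the PGI-C hypothesis unstated and still provides no interval, while calling the trial one of non-inferiority and equivalence.

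A reader might infer more than the documents support, in four ways:

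- **That the investigators plan to read p > 0.05 as non-inferiority.** No sentence says so. The misreading is a risk the plan leaves open, not a rule it adopts.
- **That 30 points is the plan's limit for PGI-C.** It is set for a 25% ESS reduction with an assumed 80% rate. Its use here is illustrative.
- **That non-significance is the expected result at a 30-point deficit.** For chi-square it stays below half at every pair of rates in the table. Fisher exceeds half at 22 per arm for the rate pairs from 80% v 50% down to 60% v 30%, but not at 90% v 60% or 40% v 10%. Because 22 per arm is the completer target and dropouts are kept by carrying the last observation forward, the analysed sample may be larger, which lowers the figures.
- **That the adverse-event comparisons share the error.** They do not, since no non-inferiority hypothesis is stated for them.

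**Conclusion.** The point stands as a mismatch between framing and method for the secondary PGI-C outcomes. They are placed under analyses similar to a non-inferiority primary, yet the only tests named cannot support non-inferiority or equivalence, and no PGI-C margin or interval is given. That conclusion does not depend on any assumed rate.

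The size does depend on assumptions: a 30-point PGI-C deficit, a two-sided 5% level, and 22 analysed per arm. On these, non-significance occurs in about 34% to 60% of trials across the base rates and tests examined; at 27 per arm with 80% versus 50% it is 34% to 45%. Because it concerns secondary outcomes and the misreading is possible rather than planned, this is something that should be corrected, not a flaw that undermines the trial.

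**What to change.** For each PGI-C outcome, report the between-arm difference in responder proportion with a two-sided confidence interval suited to small samples, for example Newcombe. Then state which of two purposes applies:

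- If non-inferiority is to be claimed for PGI-C, prespecify and justify a margin for PGI-C itself, with its significance level and direction, and judge the claim only by the confidence limit.
- If not, label chi-square or Fisher as a test of difference, say which will be used when, and state that p > 0.05 will not be read as similarity.

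The cost is one or two sentences in the Statistical Analysis section and minor analysis work, with no new data or participants. The downside is that the intervals will be wide. With 11/22 responders in both arms, the Newcombe 95% interval is ±√(0.193² + 0.193²), or about ±27 points. That width is the precision the trial actually has.
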